- t. Subjects will have an MRI-PDFF performed at each indicated timepoint unless it presents a logistical or physical hardship to the subject. MRI-PDFF will not be performed at select sites. The Baseline MRI-PDFF is to be performed during Screening or at Baseline before study drug dosing on Day 1. MRI-PDFF is not required at Early Termination if a subject has completed less than 22 weeks of study treatment.
- u. CAP and FAST scores will be measured each time a FibroScan is performed (unless the enrolling study site does not have the capability to measure CAP).
- v. Fasting lipid panel includes LDL-C, vLDL, HDL-C, non-HDL-C, total cholesterol, triglycerides, ApoB, and Lp(a) particles.
- w. Fasting metabolic panel includes insulin and NEFA. HOMA-IR and adipo-IR are to be calculated from fasting insulin, fasting glucose (see footnote p), and fasting NEFA, as applicable. An analysis of bile acid will also be performed at Baseline, Week 26, Week 52, and/or at Early Termination.

- x. Fibrosis biomarkers include ELF (TIMP-1, PIIINP, and HA), PRO-C3, FIB-4, and potentially other markers.
- y. NASH biomarkers include CK-18, adiponectin, FGF-21, and other chemokines/cytokines relevant to NASH.
- z. Alcohol biomarkers will include PEth and may also include: GGT, MCV, ALT/AST, CDT, and FAEE.
- aa. Blood samples for lipidomic biomarkers will be collected in all subjects and analysis will include tripalmitin, ceramides, bile acids, diacylglycerols, and other classes of metabolites.
- bb. The lipoprotein substudy will be conducted in approximately 30 or more subjects. Provision of blood samples for the lipoprotein substudy is voluntary.
- cc. Additional spot urine and blood samples will be collected at specified time points and stored for potential future analyses for biomarkers relevant to NAFLD/NASH. These samples will not be used for genetic analysis or for creation of cell lines. Providing spot urine and blood samples for storage is voluntary.
- dd. [REDACTED]
- ee. [REDACTED]
- ff. [REDACTED]

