8.2. Subject Exclusion Criteria

Subjects meeting any of the following criteria are not eligible for enrollment into the study.

1. History of harmful alcohol intake for a period of more than 3 consecutive months within 1 year prior to Screening in the judgement of the Investigator.
2. Active substance abuse, including inhaled or injected substances (cocaine and other illegal/banned substances; any opiate, amphetamine, or benzodiazepine for which the subject does not have an existing prescription), within 1 year prior to Screening (note that recreational cannabis/tetrahydrocannabinol use is permissible).
3. Patient-reported or medically documented gain or loss of >5% of body weight in the 6 months prior to Baseline (Day 1) or >10% of body weight in the 12 months prior to Screening.
4. Prior or planned (during the study period) bariatric surgery that may interfere with study drug absorption (e.g., roux-en-Y gastric bypass); gastroplasty and gastric reduction surgery are acceptable.
5. Type 1 diabetes mellitus by history.
6. Positive SARS-CoV-2 polymerase chain reaction (PCR) test within 30 days prior to the Baseline (Day 1) visit date or history of hospitalization for COVID-19 <6 months prior to the Screening visit date. Note that previous COVID-19 infection alone is not exclusionary, and COVID-19 vaccination is allowed. Infection and/or vaccination must be documented as medical history and/or concomitant medication, respectively.
7. Known positivity for HIV infection or positive HIV antibody result at Screening.
8. Positive hepatitis B virus antigen (HBsAg) result at Screening.
9. Positive hepatitis C virus (HCV) RNA test at Screening; however, subjects with chronic HCV infection and liver disease who were treated with anti-HCV therapy and achieved a sustained virologic response at least 2 years prior to Screening are not prevented from study participation.
10. Uncontrolled T2DM, defined as HbA1c >9.5% at Screening.
11. Serum LDL-C concentration at Screening >190 mg/dL, and the subject has been taking LDL-C-lowering treatment for \geq 30 days prior to Screening.
12. ALT and/or AST result $>5 \times$ the upper limit of normal (ULN) at Screening. One repeat test may be allowed within 7 days of receipt of the result at the discretion of the Investigator.
13. Alkaline phosphatase (ALP) result $\geq 2 \times$ ULN at Screening.

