9.7.1. Excluded Medications

The following medications and treatments are prohibited during study participation.

- Any investigational agent or device other than TVB-2640.
- Strong inhibitors or inducers of CYP3A4. (Refer to the following for examples: <http://www.fda.gov/drugs/developmentapprovalprocess/developmentresources/druginteractionslabeling/ucm093664.htm>.)
- Drugs historically associated with risk of development of NAFLD (e.g., amiodarone, methotrexate, systemic glucocorticoids [unless used at physiologic replacement doses for treatment of confirmed adrenal insufficiency], tetracyclines, tamoxifen, estrogens at doses greater than those used for hormone replacement, anabolic steroids [except for testosterone preparations used at physiologic replacement doses for treatment of documented/confirmed hypogonadism], valproic acid, and other known hepatotoxins) for more than 12 consecutive months at any time during the 5 years prior to the Screening visit date.
 - Short courses of systemic glucocorticoids may be allowed to treat acute illnesses.
- GLP-1 agonist (e.g., semaglutide), SGLT2 inhibitor (e.g., empagliflozin, canagliflozin), vitamin E at a daily dose >400 IU, and/or thiazolidinediones (TZD) (e.g., pioglitazone) unless on a stable daily dose for at least 6 months prior to the Screening visit date. Subjects who provide a historical Screening liver biopsy specimen to determine study eligibility should have been on a stable dose of these medications for at least 12 months prior to the Baseline [Day 1] visit date.
- Vitamin E at a daily dose >400 IU, and/or thiazolidinediones (TZD) (e.g., pioglitazone) should not be initiated after the Screening liver biopsy is performed.
- A complex OAD regimen (3 or more OADs [except for a GLP-1 agonist or a SGLT2 inhibitor]e.g.), unless:
 - on stable doses for at least 3 months prior to the Screening visit date and/or
 - used for uncontrolled diabetes management that is not responsive to optimized doses of other classes of anti-diabetic medications during the double-blind Treatment period.

- Insulin dose adjustment >10% (increase or decrease). (Subjects receiving insulin at Baseline [Day 1] who require a >10% dose adjustment for the management of T2DM are to be discontinued from the study.)
- Introduction of a GLP-1 agonist for weight loss during the double-blind Treatment period is prohibited.

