9.7.2. Permitted Medications

Medications and treatments other than those specified in Section [9.7.1](#) are permitted during the study. Subjects should be closely monitored, and treatment is to be instituted for disease-related symptoms, as appropriate.

If a subject receives a vaccine, including the COVID-19 vaccine, details regarding that vaccine should be recorded as a concomitant medication(s), including manufacturer, dose, and dates of each injection. Any vaccine-related reactions should be recorded as described in Section [12.2](#).

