11.1.5.1. Lipid and Metabolic Panel, Glycosylated Hemoglobin, and Lipoprotein Particle Size

A fasting blood sample for lipid and metabolic panels as well as HbA1c is to be collected. Subjects are to fast overnight for at least 9 hours prior to collection of the fasting sample (water is permissible).

The following parameters are to be determined:

- **Lipid Panel:** LDL-C, vLDL (very low density lipoprotein cholesterol), high density lipoprotein cholesterol (HDL-C), non-HDL-C, total cholesterol, triglycerides, apolipoprotein B (ApoB), and lipoprotein (a) (Lp[a]) particles.
- **Metabolic Panel:** Insulin and non-esterified fatty acid (NEFA). Homeostatic model assessment insulin resistance (HOMA-IR) and adipose tissue insulin resistance index (adipo-IR) are to be calculated from fasting insulin, fasting glucose (see Section [12.1.5](#)), and fasting NEFA, as applicable. An analysis of bile acid will also be performed at Baseline, Week 26, Week 52, and/or at Early Termination.
- **HbA1c**
- **Lipoprotein Particle Size Analysis** by nuclear magnetic resonance (NMR) will be performed for a subset of subjects.

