- Steatosis corrected qFibrosis – continuous value
- Steatosis corrected qFibrosis – stage
- Change from Baseline in metabolic parameters, including fasting insulin, fasting glucose, HOMA-IR, adipo-IR, and HbA1c levels at Weeks 26 and 52 and at each study visit.
- Change from Baseline in FGF-21, adiponectin, and other NASH biomarker levels at Weeks 26 and 52 and at each study visit.
- Change from Baseline in FibroScan Liver Stiffness Measurement (kPa) and CAP score results at Weeks 26 and 52.
- Change from Baseline in PRO-C3 and other fibrosis biomarkers at Weeks 4, 13, 26, and 52.
- Change from Baseline in ELF score at Weeks 26 and 52.
- Plasma concentrations of TVB-2640 at Weeks 1, 4, 13, 26, and 52.
- Proportion of subjects with histological improvement at Week 52 in NAS (i.e., ≥ 2 points improvement in NAS with ≥ 1 point improvement in ballooning or inflammation) and without worsening of fibrosis (by NASH CRN fibrosis score)
- Proportion of subjects with resolution of steatohepatitis and no worsening of liver fibrosis (by NASH CRN fibrosis score). Resolution of steatohepatitis is defined as absence of fatty liver disease or isolated or simple steatosis without steatohepatitis and a NAS of 0 or 1 for inflammation, 0 for ballooning, and any value for steatosis.

The exploratory efficacy and pharmacodynamics endpoints are:

- Proportion of MRI-PDFF $\geq 30\%$ responders at Week 52 who have ≥ 17 U/L reduction in ALT.
- Change from Baseline in FAST score at Weeks 26 and 52.
- Change from Baseline in Agile 3+ score at Weeks 26 and 52.

The formula from Sanyal et al (2023) for the Agile 3+ score is:

$$\text{Agile 3+} = e^{\text{logit}(p_{F \geq 3})} / (1 + e^{\text{logit}(p_{F \geq 3})})$$

with

$$\text{logit}(p_{F \geq 3}) = -3.92368 + 2.29714 \times \ln(\text{LSM}) - 0.00902 \times \text{PLT} - 0.98633 \times \text{AAR}^{-1} + 1.08636 \times \text{Diabetes status} - 0.38581 \times \text{Sex} + 0.03018 \times \text{Age}$$

Where ln is natural log; LSM=Liver Stiffness Measurement (kPa) by vibration-controlled transient elastography (VCTE); AAR=AST/ALT ratio; PLT=platelets (G/L); Sex: male=1, female=0; and Diabetes status: yes=1, no=0.

- Change from Baseline in levels of select fibrosis biomarkers (e.g., TIMP-1) at Weeks 4,

13, 26, and 52.

- Change from Baseline in levels of lipidomic/metabolomic biomarkers (e.g., tripalmitin, ceramides, bile acids, diacylglycerols, and other classes of metabolites) at Weeks 4, 13, 26, and 52.

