Proportion of subjects experiencing resolution of steatohepatitis and no worsening of liver fibrosis (by NASH CRN fibrosis score). Resolution of steatohepatitis is defined as absence of fatty liver disease or isolated or simple steatosis without steatohepatitis and a NAS of 0 or 1 for inflammation, 0 for ballooning, and any value for steatosis at Week 52.	
 • Stage of fibrosis at baseline (F2 or F3) • GLP-1 at baseline (Yes or No) [1] • SGLT2 at baseline (Yes or No) [2]
Proportion of subjects with histological improvement (decrease) at Week 52 in NAS by ≥ 1 point.	
 • Stage of fibrosis at baseline (F2 or F3) • GLP-1 at baseline (Yes or No) [1] • SGLT2 at baseline (Yes or No) [2]
Proportion of subjects with histological improvement (decrease) at Week 52 in NAS by ≥ 2 points.	
 • Stage of fibrosis at baseline (F2 or F3) • GLP-1 at baseline (Yes or No) [1] • SGLT2 at baseline (Yes or No) [2]
Change from Baseline in ALT, AST, and GGT at Weeks 26 and 52 and at each study visit.	
 • Stage of fibrosis at baseline (F2 or F3) • T2DM at baseline (Yes or No)
Change from Baseline in LDL-C and other lipid levels (including LDL/HDL ratio) at Weeks 26 and 52 and at each study visit.	
 • T2DM at baseline (Yes or No) • Statin use at baseline (Yes or No) [3]
Changes from Baseline in metabolic parameters, including fasting insulin, fasting glucose, HOMA-IR, adipon-IR, and HbA1c levels at Weeks 26 and 52 and at each study visit.	
 • T2DM at baseline (Yes or No)
Change from Baseline in FibroScan (Liver Stiffness Measure (kPa)) and CAP score results at Weeks 26 and 52.	
 • $\geq 30\%$ reduction in MRI-PDFF from baseline to Week 52 (yes or no) – includes subjects with $\geq 8\%$ liver fat content at Baseline • $\geq 50\%$ reduction in MRI-PDFF from baseline to Week 52 (Yes or No) – includes subjects with $\geq 8\%$ liver fat content at Baseline

Endpoint	Subgroups
Selected Exploratory Endpoints	
Change from Baseline in FAST score at Weeks 26 and 52.	
 • 30% reduction in MRI-PDFF from baseline to Week 52 (yes or no) – includes subjects with $\geq 8\%$ liver fat content at Baseline • $\geq 50\%$ reduction in MRI-PDFF from baseline to Week 52 (Yes or No) – includes subjects with $\geq 8\%$ liver fat content at Baseline

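### Fasting insulin, HOMA-IR and adipo-IR are tested in all ITT subjects, including those on insulin at Baseline, in whom these values do not validly reflect insulin resistance

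*SAP*

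**What the plan says.** - **Endpoint.** SAP 5.1 lists "Change from Baseline in metabolic parameters, including fasting insulin, fasting glucose, HOMA-IR, adipo-IR, and HbA1c levels at Weeks 26 and 52". It is endpoint 19 in SAP 7.4 and is tested two-sided. SAP 7.3 gives no multiplicity control for it.
- **Derivation.** The schedule footnote in the protocol synopsis states: "HOMA-IR and adipo-IR are to be calculated from fasting insulin, fasting glucose (see footnote p), and fasting NEFA, as applicable". Protocol 11.1.5.1 repeats this.
- **Who enrols.** Protocol 8.2 excludes type 1 diabetes and "Uncontrolled T2DM, defined as HbA1c >9.5% at Screening", but not insulin use. Protocol 9.7.1 expects insulin users: "Subjects receiving insulin at Baseline [Day 1] who require a >10% dose adjustment for the management of T2DM are to be discontinued".
- **Insulin during the study.** Protocol 9.7.1 lists an insulin dose change above 10%, up or down, as prohibited. The section ends by saying that subjects who need such treatment are to be discontinued. Protocol 8.3 makes need for a prohibited medication a ground on which the investigator may withdraw a subject. Protocol 9.7.2 then permits "Medications and treatments other than those specified in Section" 9.7.1. No sentence addresses a first start of insulin.
- **Analysis.** SAP section 6 makes ITT the basis for all efficacy analyses. The ANCOVA and MMRM in SAP 9.2 include T2DM status, treatment and the baseline value, with no term for insulin. SAP section 7 uses all data up to withdrawal, and SAP 7.10 maps early-termination values to a scheduled visit.
- **Subgroup.** For "Changes from Baseline in metabolic parameters, including fasting insulin, fasting glucose, HOMA-IR" and the other parameters in that row, SAP 7.2 gives only T2DM yes or no. The diabetes-medication subgroup is assigned to the co-primary and selected safety endpoints.

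**The concern.** HOMA-IR multiplies insulin by glucose, and adipo-IR uses insulin with NEFA. Both read high insulin as resistance, which presumes that the insulin measured is the subject's own secretion responding to need. That presumption fails in a subject who injects insulin. If the assay detects the injected product, the value follows its dose and timing. If it does not, the value reflects secretion suppressed by the injection. The direction of the error differs, but in neither case is the result a valid index of resistance.

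Nothing in the plan removes, flags or separately analyses these values, so three parameters of a secondary endpoint mix two different quantities. Two consequences have to be kept apart. Users whose dose is stable can add noise. Subjects who start insulin after Baseline shift their own change score, and an imbalance in starts between arms would shift the comparison.

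**Working it through.** **The plan's own figure.** No effect size, SD or power is stated for endpoint 19. The only design figure is the 162 for the primary endpoint, and it reproduces with the unpooled normal approximation at 40% vs 20%, one-sided 0.05, 80% power and 2:1 allocation: n on placebo = (1.645 + 0.842)² × (0.20×0.80 + 0.40×0.60/2) / 0.20² = 6.18 × 0.28/0.04 = 43.3, so 44. Then 44 + 88 = 132, and 132/(1 − 0.185) = 162. It is used here only for arm sizes (108/54 randomised, 88/44 after dropout).

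**Step 1: stable Baseline use and precision.** All inputs are assumptions. Let a share p use insulin, and let the variance of the HOMA-IR change in users exceed that in non-users by a factor 1 + r. Ignoring covariate adjustment, SE with users kept divided by SE with users removed is √[(1 − p)(1 + p·r)]. At p = 0.15:

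- a ratio of 1.0 needs r = (1/0.85 − 1)/0.15 = 1.2;
- a ratio of 1.1 needs r = (1.21/0.85 − 1)/0.15 = 2.8;
- a ratio of 1.5 needs r = (2.25/0.85 − 1)/0.15 = 11.0.

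The answer therefore depends on how much the injected contribution varies within a subject between visits. Two sets of simulations at 15% use, with different residual variance, give:

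| Injected contribution from visit to visit | Set 1: SE kept / removed | Set 2: SE kept / removed |
|---|---|---|
| Redrawn (nearly) independently | 0.73/0.52 = 1.40 | 0.65/0.42 = 1.55 |
| Subject's own level, 30% variation | 0.65/0.52 = 1.25 | 0.58/0.42 = 1.38 |
| Subject's own level, 15% variation | 0.54/0.52 = 1.04 | 0.45/0.42 = 1.07 |

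A further ANCOVA simulation (88/44; median endogenous insulin 22 µU/mL; 60% T2DM; injected insulin adding a median 40 µU/mL with 40% timing variation; 1,500 runs) gives mean 95% CI widths of 3.85 HOMA units with 15% users and 2.36 with none. Scaling the latter for the loss of 15% of subjects gives 2.36/√0.85 = 2.56, and 3.85/2.56 = 1.50.

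**Step 2: type I error without an imbalance in starts.** Same ANCOVA simulation, no drug effect, two-sided 5%: 5.6% with no users, 5.3% with 15% stable users, 5.8% with 15% users and 5% starting in each arm. The Monte Carlo SE is √(0.05×0.95/1500) = 0.6 points, so all three are compatible with 5%.

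**Step 3: unequal starts.** False difference = (start rate on placebo − start rate on drug) × HOMA-IR shift per starter. With glucose 7.5 mmol/L falling 10% after a start and the assay detecting injected insulin, the shift is added insulin × 7.5 × 0.9/22.5 = 0.3 × added insulin.

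- Assumed starts of 3% vs 9%: 0.06 × 0.3 × 40 = 0.72 HOMA units. The simulations gave 0.6 to 0.8.
- Added insulin of 20 to 80 µU/mL: 0.36 to 1.44 units.
- In subjects: 0.03 × 108 = 3.2 on drug against 0.09 × 54 = 4.9 on placebo.

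In the ANCOVA simulation with the same 6-point gap (2% vs 8%), the two-sided false-positive rate was 8.4% (+40 µU/mL, 15% Baseline users), 12.3% (+80, 15% users) and 15.4% (+40, no Baseline users). A Wilcoxon test gave 6% to 8%. Protocol 13.2.2 planned that test for these endpoints; SAP 9.2 does not carry it, and SAP section 11 does not list its removal.

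If the assay does not detect injected insulin, starters' values fall instead and the sign reverses. It also reverses if the drug arm starts more often. Adipo-IR was not simulated, but it takes its error from the same insulin value.

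**The case against.** Four stronger readings are tempting, and the documents do not support them.

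- **Insulin starts are plainly permitted.** A reader might infer this because 9.7.1 does not name a start and 9.7.2 permits what is unlisted. But 9.7.1 prohibits an insulin change above 10% in either direction, and a start from zero can be read as an increase. The closing sentence of 9.7.1 and the withdrawal ground in 8.3 could then apply. The text is ambiguous. Even on the strict reading, values obtained before or at withdrawal can enter under SAP sections 7 and 7.10, so exposure is limited but not removed.
- **Measured insulin includes injected insulin, so HOMA-IR is pushed up.** The assay is not described, and Protocol 11.1.5 leaves sample handling details to the Laboratory Manual. The invalidity stands either way; its direction does not.
- **Baseline users add large noise.** The 10% rule keeps doses stable, and a stable contribution largely cancels in a change score. The larger ratios need nearly independent values at each visit.
- **The plan favours TVB-2640.** With equal starts there is no bias, and no start rate is documented.

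There are also partial safeguards. The models adjust for T2DM. The T2DM-no subgroup should be largely free of Baseline insulin users, although the T2DM-yes subgroup still mixes users and non-users. SAP 8.6 summarises concomitant medication by arm, so an imbalance could be noticed, though not by visit.

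The objection to deleting values after a start also stands. It assumes missing at random, while starts probably follow worsening. When starts were linked to rising HOMA-IR, deletion left 0.06 to 0.23 HOMA units against the drug. That suits a sensitivity analysis, not the main one.

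**Conclusion.** The gap is established from the text: three parameters of endpoint 19 are analysed in all ITT subjects although some may be on insulin at Baseline, and in those subjects the values do not validly measure insulin resistance. The size is not established, because the documents give neither the share on insulin nor any start rate.

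Under an assumed 15% stable use, the cost is precision, with an SE about 1.1 to 1.5 times that with users removed and type I error near 5%. A false arm difference arises only if starts differ between arms, about 0.6 to 0.8 HOMA units at an assumed 3% vs 9%, in a direction that depends on the assay and on which arm starts more. It would be wrong to conclude that the plan is biased towards the drug.

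The effect is confined to three secondary parameters. The co-primary endpoints and the sample size are untouched. The change is still worth making because it is cheap and, if made after unblinding, would look data-driven.

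**What to change.** 1. In SAP 9.2, base the inferential analysis of fasting insulin, HOMA-IR and adipo-IR on subjects not receiving insulin at Baseline. Apply the same restriction to their T2DM subgroup table in SAP 7.2. Insulin use at Baseline precedes randomisation, so the comparison stays randomised. Protocol 9.7 already collects the medication and its dose changes, and SAP 7.2 already identifies drug classes by ATC code.
2. Keep the all-ITT analysis of these parameters as supplementary. Leave HbA1c and fasting glucose in all subjects.
3. Tabulate insulin use, including on-study starts, by arm and visit.
4. Add a sensitivity analysis that sets values after an on-study insulin start to missing, with its missing-at-random assumption stated.
5. Reconcile Protocol 8.3, 9.7.1 and 9.7.2 on whether an insulin start falls under the prohibited adjustment. This point does not say which rule is right.
6. Record the change in SAP section 11 before unblinding.

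The cost is SAP wording, one filter and one table. The downside is a smaller n for three secondary parameters: at an assumed 15% use, about 0.85 × 108 = 92 and 0.85 × 54 = 46 subjects before dropout.

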5.2. Safety

The safety endpoints are:

- Adverse events (AEs) throughout the study.
- Electrocardiograms (ECGs) at Weeks 26 and 52.
- Vital signs at each study visit.
- Physical examination findings at each study visit.
- Eye examination findings at each study visit.
- Hematology and coagulation results at each study visit.
- Liver aminotransferase levels at each study visit.
- Clinical chemistry results at each study visit.
- Urinalysis results at each study visit.

- Pregnancy test results throughout the study.
- Prior and concomitant medications throughout the study.
- Results of anthropometric measurements at Week 52.

